2. An interim OS analysis will be performed at Analysis #1 with all **observed** death events, regardless if H_2 is rejected. In the event when Analysis #2 occurs prior to Analysis #1, then it will include an interim analysis to test H_2 for PFS (using all PFS events) and, if H_2 is not rejected, it will be tested again at the planned time for Analysis #1. However, if the projected time for achieving 407 PFS events is within 4 months from the projected 282 OS events time, then Analysis #2 will be combined with Analysis #1 and be performed at Analysis #1 using all death events with PFS times censored after the 407th PFS event.
3. At each of the **5** planned analysis times, it will be considered an interim analysis of iCRR and iPFS, rather than the primary analysis, if the maximum information has not been reached for the respective endpoint at that time. For example, if H_3 is tested in an analysis that includes fewer than 256 iPFS events, then it will be an interim analysis of iPFS that includes all observed events; otherwise, it will be the primary analysis with all iPFS times censored after the date of the 256th event. If all randomized subjects do not have at least 36 weeks follow-up in an analysis, then it will be an interim analysis for iCRR only including those subjects with at least 36 weeks follow-up; otherwise, it will be the primary analysis and include all randomized subjects. With the exception of PFS, the hypothesis for an endpoint may be re-tested after its primary analysis using its primary analysis data if alpha is subsequently propagated to it from the rejection of another hypothesis.
4. Assuming Analysis #1 is before Analysis #2, and at Analysis #1 the null hypothesis of PFS (H_2) is rejected, the hypotheses H_3 and H_4 will be tested. H_1 will be tested at Analysis #1 regardless of whether H_2 is rejected. The iPFS (H_3) and iCRR (H_4) can be tested if H_2 is not rejected but H_1 is significant. Likewise, OS subgroup (H_5) can be tested at Analysis #1 if any of the following set of hypotheses are rejected: (1) H_2 and H_3 ; (2) H_2 and H_4 ; (3) H_1 and H_3 ; or (4) H_1 and H_4 .
5. If projections indicate 256 iPFS events will occur in the same timeframe as either Analysis #1 or Analysis #2, then the option will be considered to extend the data cutoff to include all 256 iPFS events. In this event, Analysis #1 will have PFS times censored after the 407th PFS event and Analysis #1 or #2 will include all OS events.

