6. The OS hypothesis (H_1) will be tested at Analyses #1-4 with all (Analysis #1) or required number (Analysis #2, Analysis #3, **and Analysis #4**) of events in the absence of its prior rejection (or futility at Analysis #2).
7. The OS subgroup hypothesis (H_5) will be tested at the first and all subsequent analysis times when alpha can be propagated to it from the rejection of H_1 or H_2 followed by H_3 and/or H_4 . All OS events in the subgroup at the end of 5 years follow-up will be used if 208 events have not been observed. If H_1 is not rejected by Analysis #4, it will be tested again using events at Analysis #4 if alpha can be propagated from the rejection of H_5 at Analysis #5.
8. Likewise, H_3 and H_4 may be re-tested if not rejected by their primary analysis using their respective primary analysis data if H_1 is subsequently rejected.

Table 3 illustrates possible hypothesis tests at the 5 planned analyses.

Table 3. Study Analyses and Possible Hypothesis Tests

Analysis	Timing	Hypothesis Tested (Analysis Type)				
		H ₁ (OS)	H ₂ (PFS)	H ₃ (iPFS)	H ₄ (iCRR)	H ₅ (OS subgroup)
#1	407 PFS events	(IA)	(PA)	If reject H ₁ or H ₂ (IA if < 256 events)	If reject H ₁ or H ₂ (IA if includes fewer than all randomized)	If reject H ₂ and either H ₃ or H ₄ , or reject H ₁ and either H ₃ or H ₄ (IA if < 208 events)
#2	282 OS events	(IA)	n/a (IA if Analysis #2 is performed first)	If reject H ₁ or H ₂ (PA on first 256 events)	If reject H ₁ or H ₂ (PA if includes all randomized)	If reject H ₂ and either H ₃ or H ₄ , or reject H ₁ and either H ₃ or H ₄ (IA if < 208 events)
#3	315 OS events	(IA)	n/a	If reject H ₁ or H ₂ (PA on first 256 events)	If reject H ₁ or H ₂ (PA if includes all randomized)	If reject H ₂ and either H ₃ or H ₄ , or reject H ₁ and either H ₃ or H ₄ (IA if < 208 events)
#4	346 OS events	(PA)	n/a	See Analysis #2 & #3 above	See Analysis #2 & #3 above	See Analysis #2 & #3 above
#5	Earlier of 208 OS events in subgroup or 5 years minimum follow-up	If reject H ₂ previously and H ₅ (PA at first 346 events)	n/a	See Analysis #2 & #3 above	See Analysis #2 & #3 above	See Analysis #2 & #3 above (PA)

iCRR = complete response rate (by modified irRC-RECIST); iPFS = progression free survival (by modified irRC-RECIST); H = hypothesis; IA = interim analysis; n/a = not applicable; OS = overall survival; PA = primary analysis; PFS = progression free survival

Futility Analysis for OS

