In the event of inadvertent Suspected Unexpected Serious Adverse Reaction (SUSAR) unblinding, an additional sensitivity analysis for PFS will be performed to assess the potential effect of the unblinding, by removing all event data after the date of the SUSAR unblinding from the analysis.

For the iPFS endpoint, analyses will be repeated if applicable imputing an event at the time of a last overall visit response of iPD that was not confirmed as required per modified irRC-RECIST.

Additionally, to assess the robustness of the PFS and iPFS primary and supportive analyses given the potential for bias related to potential informative censoring, the analyses noted for OS potential censoring in [Section 10.5.4.2](#) will be repeated for PFS and iPFS. Censoring times will be classified as (1) administrative (random) if within 91 days (corresponding to maximum lag time allowable between tumor assessments) of the analysis data cutoff date or otherwise (2) informative.

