10.5.4.2 OS Sensitivity Analyses

The following set of analyses will be used to assess the robustness of the OS primary analysis given the potential for bias related to informative censoring, and also to assess the impact of subsequent anti-cancer therapy.

- OS potential informative censoring will be assessed with a competing risks analysis utilizing the Fine-Gray proportional subdistribution hazards model ([Fine, 1999](#); [Gray, 1988](#)) (see code fragment in [Appendix C](#)). Censoring times will be classified as (1) administrative (random) if within 140 days (corresponding to maximum lag time allowable between long term follow up assessments) of the analysis data cutoff date or otherwise (2) informative. Type (2) censoring will be defined as a competing risk event. Gray's test will be performed and the Fine-Gray treatment HR with 95% CI will be calculated stratified as per dual primary efficacy endpoints.
- The impact of subsequent anti-cancer therapy on OS will be assessed by summarizing the incidence by treatment arm of selected anti-cancer therapies with potential OS benefit, the timing of such therapies among subjects that received it, and K-M and treatment HR estimates of time to first use among all subjects. OS analyses will be repeated in which OS is censored at the first selected anti-cancer therapy.
- Since this analysis may introduce bias due to dependent censoring, the OS effect will also be estimated with an inverse probability censoring weighting (IPCW) method (see code fragment in [Appendix C](#)) that incorporates a pre-specified covariate history (eg, grouped stage of disease (not IVRS), LDH, SLD, change in ECOG performance score, *BRAF* mutation (not IVRS), PD-L1, **and** time to progression per irRC-RECIST.) and outcomes up to the start of subsequent anti-cancer therapy ([Robins et al., 2000](#))

In the event of inadvertent SUSAR unblinding, an additional sensitivity analysis for OS will be performed to assess the potential effect of the unblinding, by removing all event data after the date of the SUSAR unblinding from the analysis.

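### The 91-day test for informative censoring counts back from the analysis data cutoff, but the iPFS primary analysis stops at the 256th event; if the two dates are more than 91 days apart, nearly all censored iPFS subjects are coded as dropouts

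*SAP*

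**What the plan says.** SAP 10.5.4.1 repeats the OS informative-censoring analysis for PFS and iPFS. Its rule begins "Censoring times will be classified as (1) administrative (random) if within 91 days", and the window in full is "within 91 days (corresponding to maximum lag time allowable between tumor assessments) of the analysis data cutoff date or otherwise (2) informative". SAP 10.5.4.2 gives the consequence for the Fine-Gray model: "Type (2) censoring will be defined as a competing risk event".

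SAP 8.1.4 item 3 sets a different end point for iPFS. With fewer than 256 iPFS events the analysis is an interim one on all observed events; "otherwise, it will be the primary analysis with all iPFS times censored after the date of the 256th event". SAP Table 3 plans this form at Analyses #2 and #3: "PA on first 256 events".

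The data cutoff belongs to the analysis time, not to the endpoint. SAP 10.1 ties it to each analysis time, and SAP 8.1.4 rules out a separate snapshot per endpoint.

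PFS can also be truncated. Under item 2, when Analyses #1 and #2 are combined, the analysis is "performed at Analysis #1 using all death events with PFS times censored after the 407th PFS event". Under item 5, "the option will be considered to extend the data cutoff to include all 256 iPFS events", and then "In this event, Analysis #1 will have PFS times censored after the 407th PFS event".

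**The concern.** The sensitivity analysis is meant to separate subjects lost to follow-up from subjects who were simply event-free when the analysis stopped. That needs the 91 days to be counted from the date on which follow-up for the endpoint stopped. For a truncated endpoint that is the date of the 256th (or 407th) event, but the rule counts from the analysis-wide cutoff. Nothing in either document redefines the cutoff for a truncated endpoint, and item 5 treats the cutoff and the truncation date as two separate things.

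If the dates are far apart, administrative censoring is itself coded as dropout. A hazard ratio that hardly moves could then be reported as showing robustness to informative censoring of iPFS, which is one of the five formally tested hypotheses, although dropout had never been isolated.

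**Working it through.** **The logic.** Let C be the analysis data cutoff, D the date of the 256th iPFS event, and X a subject's censoring date (last evaluable tumor assessment, not after D). Then C − X ≥ C − D. If C − D > 91 days, no event-free subject can meet the administrative criterion.

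**If the gap is 91 days or less.** Suppose the last scan falls evenly over the 84 days before D. The share of subjects still in follow-up who stay administrative is then about (91 − gap)/84: (91 − 30)/84 = 73% at 30 days and (91 − 60)/84 = 37% at 60 days.

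**Reproducing the plan's figures.**
- Window: 7 × (12 + 1) = 91 days, as stated.
- PFS cutoff, inputs from protocol 10.2.2: control PFS 0.95, 0.60, 0.49, 0.39, 0.32 and 0.30 at months 1.5, 3, 6, 12, 18 and 24, piecewise exponential; HR 0.67; 26-month enrollment with half enrolled at two-thirds of the period; 10% annual loss; N=660. The model gives 407 events at month 48.0, against month 48 in protocol Table 9.

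**Date of the 256th iPFS event.** Same model, with HR 0.60 (protocol Table 10). The control iPFS curve is not in the documents, so the PFS hazard was scaled; the multiplier is an assumption.

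| Control iPFS hazard relative to PFS | 256th event, month (N=660) | Gap to month 48 |
|---|---|---|
| 1.0 | 25.4 | (48 − 25.4) × 30.4375 = 688 days |
| 0.8 | 27.4 | 627 days |
| 0.6 | 35.7 | 374 days |
| 0.5 | 56.0 | not reached by month 48 |

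SAP Table 4 gives month 44 for the PFS analysis. The smallest gap in the first three rows would then be (44 − 35.7) × 30.4375 = 253 days. With the 692 subjects of SAP Table 5, the model puts 407 PFS events at month 38.8 and the 256th iPFS event at months 24.8 to 32.8 (multipliers 1.0 to 0.6), so the gap is at least 6.0 months. At multiplier 0.5 and N=692 the 256th event is at month 46.2, 55 days before month 48.

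**A bound from the plan's own timings.** iPFS counts every death, so iPFS events cannot be fewer than deaths. Protocol Table 12 projects 252 deaths at month 48 and 282 at month 52. Linear interpolation puts the 256th event no later than 48 + 4 × (256 − 252)/(282 − 252) = month 48.5. In that slowest case there is no truncation at Analysis #1. The gap is about 106 days at Analysis #2 (month 52) and 379 at Analysis #3 (month 61). The 106 days exceeds 91 only narrowly and rests on projected dates.

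**How many are real dropouts (N=660, simulated).** At multiplier 1.0, about 33 of 376 censored subjects (9%; not everyone is enrolled by month 25). At 0.6, about 75 of 404 (19%), where 404 = 660 − 256. The written rule codes essentially all of them as informative. Counting from D works: at N=692 and multiplier 0.6, about 372 of 436 become administrative, leaving 64 informative against about 68 real dropouts.

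**Effect on the estimate.** The like-for-like comparison is Fine-Gray with only real dropouts competing against Fine-Gray as written (N=692, non-informative dropout):

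| Multiplier | Only dropouts competing | As written |
|---|---|---|
| 1.0 | 0.602 | 0.621 |
| 0.8 | 0.602 | 0.611 |
| 0.6 | 0.606 | 0.608 |
| 0.5 | 0.601 | 0.601 |

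The shift is 0.00-0.02, against a standard error of the log HR of about 2/√256 = 0.125.

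**The case against.** The strongest reply is that the plan never says when the 256th iPFS event will occur, so the gap is a projection from an assumed curve. iPFS could accrue slowly: progression needs confirmation, and progression of non-measurable lesions alone does not count. SAP 8.1.4 itself allows for fewer than 256 events at Analysis #1, and item 5 allows the cutoff to be moved to the 256th event. SAP Table 5 does show 256 of 256 at the PFS analysis, but as an example and without a date. This stands: a reader might infer that every censored iPFS subject is always misclassified, and the documents support that only when the gap exceeds 91 days.

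A reader might also take item 2 to permit a PFS cutoff four months past the 407th event, which would misclassify PFS too. The text does not say so. The four months is a window for deciding whether to combine two analyses, and the combined analysis is performed at Analysis #1, defined by 407 PFS events. Item 5 could create a PFS gap, but only if the 256th iPFS event had not yet occurred; the iPFS gap would then be about zero.

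Finally, SAP 10.5.4 makes all sensitivity p-values descriptive, and 10.5.4.1 has other iPFS robustness analyses that do not use the 91-day rule. That limits the consequence but does not make the reference date right.

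**Conclusion.** The point holds in conditional form. Whenever iPFS is truncated more than 91 days before the data cutoff, the rule codes essentially all event-free subjects as informative, although only a minority are real dropouts. Such a gap is expected if the control iPFS hazard is 60-100% of the PFS curve. It is not certain: near 50% the dates nearly coincide or reverse, and the problem does not arise for an interim iPFS analysis or if item 5 sets the cutoff at the 256th event. For PFS it arises only if the cutoff is actually set later than the 407th event.

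The damage is to interpretation: an inflated count of informative censorings, and a check that does not isolate dropout. It would be wrong to infer a material bias in the hazard ratio or any threat to the formal tests. Nor was an error shown in the separate rule that moves assessment times.

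**What to change.** In SAP 10.5.4.1, count the 91 days from the earlier of the analysis data cutoff date and the endpoint's own truncation date: the 256th iPFS event, or the 407th PFS event where PFS times are truncated there. Where the dates coincide, nothing changes. The cost is one SAP sentence and one date variable in the program, best settled before unblinding.

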10.5.4.2 OS Sensitivity Analyses

The following set of analyses will be used to assess the robustness of the OS primary analysis given the potential for bias related to informative censoring, and also to assess the impact of subsequent anti-cancer therapy.

- OS potential informative censoring will be assessed with a competing risks analysis utilizing the Fine-Gray proportional subdistribution hazards model ([Fine, 1999](#); [Gray, 1988](#)) (see code fragment in [Appendix C](#)). Censoring times will be classified as (1) administrative (random) if within 140 days (corresponding to maximum lag time allowable between long term follow up assessments) of the analysis data cutoff date or otherwise (2) informative. Type (2) censoring will be defined as a competing risk event. Gray's test will be performed and the Fine-Gray treatment HR with 95% CI will be calculated stratified as per dual primary efficacy endpoints.
- The impact of subsequent anti-cancer therapy on OS will be assessed by summarizing the incidence by treatment arm of selected anti-cancer therapies with potential OS benefit, the timing of such therapies among subjects that received it, and K-M and treatment HR estimates of time to first use among all subjects. OS analyses will be repeated in which OS is censored at the first selected anti-cancer therapy.
- Since this analysis may introduce bias due to dependent censoring, the OS effect will also be estimated with an inverse probability censoring weighting (IPCW) method (see code fragment in [Appendix C](#)) that incorporates a pre-specified covariate history (eg, grouped stage of disease (not IVRS), LDH, SLD, change in ECOG performance score, *BRAF* mutation (not IVRS), PD-L1, **and** time to progression per irRC-RECIST.) and outcomes up to the start of subsequent anti-cancer therapy ([Robins et al., 2000](#))

In the event of inadvertent SUSAR unblinding, an additional sensitivity analysis for OS will be performed to assess the potential effect of the unblinding, by removing all event data after the date of the SUSAR unblinding from the analysis.

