Endpoint / Hypothesis	i	Nominal $p_{i,1}$	$\alpha_{i,1}^*(w_i(1, 2, 3, 4, 5)\alpha)$	$\alpha_{i,1}^*(w_i(3, 4, 5)\alpha)$	$\alpha_{i,1}^*(w_i(5)\alpha)$	Significance at PFS PA
OS	1	0.03	0.0150	-	-	Not significant
PFS	2	0.001	0.0050	-	-	Significant
iPFS	3	0.003	0	0.0045	-	Significant
iCRR	4	0.011	0	0.00455	-	Not significant
OS subgroup	5	0.01	0	NA	0.0001	Not significant

Appendix C. Technical Detail and Supplemental Information Regarding Statistical Procedures and Programs

C.1 Cochran-Mantel-Haenszel (CMH) Statistics

```
proc freq data=data1;  
    tables <stratum> * trtgrp * response /cmh;  
run;
```

C.2 Mantel-Haenszel Common Risk difference

```
ods output CommonPdiff=cpdiff2;  
proc freq data=data1;  
    tables Gender*Treatment*Response /riskdiff(common);  
    weight Count;  
run;  
  
data cpdiff_3;  
    set cpdiff2;  
    if method='Mantel-Haenszel';  
    p_value=min(1, 2*(1-probnorm(abs(value/stderr))));  
run;
```

C.3 Clopper-Pearson Exact Confidence Interval

```
proc freq data=data1;  
    tables var1/ binomial(exact);  
    by trtgrp;  
run;
```

C.4 Fisher's Exact Test

```
proc freq data=data1;  
    tables var1 * trtgrp /exact;  
run;
```

C.5 Logistic Regression

```
/* event='1': value 1 indicating an event/response observed */  
proc logistic data=data1;  
    class trtgrp cov1 cov2 cov3;  
    model response (event='1') = trtgrp cov1;  
run;  
  
/* Stratified logistic regression */  
proc logistic data=data1;  
    class <stratum> trtgrp cov1 cov2 cov3;  
    model response (event='1') = trtgrp cov1;  
    strata <stratum>;  
run;
```

C.6 Kappa Coefficient

```
proc freq data=data1;  
  tables var1 * trtgrp /agree;  
run;
```

C.7 Wilcoxon Rank-sum Test on Continuous Response

```
proc npar1way wilcoxon data=<data>;  
  class trtpxcd;  
  var <continuous endpoint>;  
run;
```

C.8 Fine-Gray Subdistribution Proportional Hazards Model

/* The variable STATUS has three values: 0 for censored observations, 1 for subjects with event of interest (e.g. local recurrence for LRFS), and 2 for patients who experienced competing risk. */

```
proc phreg data=dat1 ;  
  class TRTGRP (order=internal ref=first) param=glm;  
  model LRFS*STATUS(0)= TRTGRP x1 x2 / eventcode=1;  
  hazardratio 'Subdistribution Hazards' TRTGRP;  
  strata randomization_strata;  
  * Delete strata statement to assess overall proportional hazards;  
  * x1, x2 are covariates.  
run;
```

C.9 Assumption of Non-Proportionality Hazards: Schoenfeld Residuals Plot

```

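### The OS informative-censoring check codes early loss to follow-up as a competing event, so it compares recorded deaths: it favours the arm with the higher loss rate and cannot respond to what happens after loss

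*SAP*

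**What the plan says.** SAP 10.5.4.2 sets out to test the OS result against informative censoring. Its method is: "OS potential informative censoring will be assessed with a competing risks analysis utilizing the Fine-Gray proportional subdistribution hazards model". The split is by calendar distance from the data cutoff: "Censoring times will be classified as (1) administrative (random) if within 140 days" of it, and informative otherwise. Then: "Type (2) censoring will be defined as a competing risk event". The output is specified as: "Gray's test will be performed and the Fine-Gray treatment HR with 95% CI will be calculated stratified as per dual primary efficacy endpoints".

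SAP 10.5.4.1 extends the check. It says that "the analyses noted for OS potential censoring in" Section 10.5.4.2 "will be repeated for PFS and iPFS", with 91 days in place of 140. The code fragment in Appendix C.8 confirms the coding: status 0 is censored, "1 for subjects with event of interest (e.g. local recurrence for LRFS), and 2 for patients who experienced competing risk".

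Other provisions that bear on the point:

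- SAP Section 6 censors OS at the last date the subject is known to be alive.
- SAP 10.5.4.2 also plans inverse probability of censoring weighting (IPCW), but only for the analysis that censors OS at the first selected subsequent anticancer therapy.
- SAP 10.5.1.1 plans follow-up summaries and plots overall and by arm, with the plots repeated for subjects with censored OS, and Clark's completeness index.
- SAP 10.5.4.1 adds, for iPFS only, an analysis that imputes an event at a last unconfirmed iPD.
- SAP 10.5.4 makes all sensitivity p-values descriptive.

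**The concern.** A competing event is one that makes the event of interest impossible. Loss to follow-up does not do that: a subject lost at month 20 can still die at month 24, and the trial simply does not see it. In a Fine-Gray model, a subject with a competing event stays in the risk set and never has the event. Applied here, every early-lost subject is carried forward as if death could no longer occur.

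Two consequences follow. If the arms lose subjects at different rates, the estimate moves in favour of the arm with the higher rate, even when the loss has nothing to do with prognosis. And because no assumption about survival after loss enters the calculation, the answer is the same whether lost subjects do as well as, or much worse than, those who stay. That second question is the one the analysis is meant to address.

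PFS has its own route into the problem. Under the phase 3 schedule (protocol Table 6), imaging stops at confirmed iPD or new anticancer therapy, while primary PFS rests on central-review modified RECIST 1.1. A subject who starts new therapy without centrally determined PD, and has no later event, is censored at the last evaluable assessment. If that lies more than 91 days before cutoff, the check treats the subject as never progressing.

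At stake is the robustness statement for OS and, by cross-reference, PFS and iPFS.

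**Working it through.** **Inputs from the documents.** Protocol 10.2.2: 660 subjects, 1:1; OS HR 0.70; 346 deaths; two-sided 0.045; control OS with median 28 months, 31% at 48 and 27% at 60 months; half of enrolment by two-thirds of the period; loss 5% per year for OS. Table 9: 26 months' enrolment.

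**Assumptions.** Loss rates that differ by arm, and the death hazard after loss (times 1, 2 or 3). The documents give neither.

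**Plan's own figures.**

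- Deaths, single look: 4 × (2.005 + 1.282)² / (ln 0.70)² = 340. With 346 deaths and the four nominal levels of protocol Table 12 (PFS not significant), cumulative power is 65.5, 75.6, 84.1 and 89.6%, against 66, 76, 84 and 90% stated.
- PFS events: 4 × (2.807 + 1.282)² / (ln 2/3)² = 407, as stated.
- Windows: 84 + 28 + 28 = 140 days; 84 + 7 = 91 days.

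None of these is in dispute.

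**Hand calculation of the mechanism.** Take equal survival in both arms, constant hazard h = ln 2 / 28 = 0.02476 per month, and harmless loss at 10% (talimogene laherparepvec) and 5% (placebo) per year: l = −ln(0.90)/12 = 0.00878 and −ln(0.95)/12 = 0.00427. Ignore the 140-day window. The cumulative incidence of recorded death is

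F(t) = h/(h + l) × [1 − exp(−(h + l)t)].

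At t = 30 months, chosen for illustration:

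- Talimogene laherparepvec: 0.738 × (1 − 0.366) = 0.468.
- Placebo: 0.853 × (1 − 0.419) = 0.496.
- True probability of death in both arms: 1 − 0.5^(30/28) = 0.524.
- Average subdistribution HR: ln(1 − 0.468)/ln(1 − 0.496) = 0.92, where the truth is 1.00.

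**Simulation.** 3000 trials per row, with the protocol's piecewise OS curve and accrual, cut at the 346th recorded death. Losses more than 140 days before cutoff stay in the risk set to the cutoff (Fine-Gray in its censoring-complete form; a log-rank test on these data stands in for Gray's test). Unstratified. T is talimogene laherparepvec, P is placebo.

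| HR before loss | Loss/yr, T vs P | Death hazard after loss | Early losses, T/P | Cox | Fine-Gray | HR with complete follow-up |
|---|---|---|---|---|---|---|
| 1.00 | 5% vs 5% | ×1 | 27/27 | 1.00 | 1.00 | 1.00 |
| 1.00 | 7.5% vs 5% | ×1 | 41/28 | 1.00 | 0.96 | 1.00 |
| 1.00 | 10% vs 5% | ×1 | 55/28 | 1.00 | 0.92 | 1.00 |
| 1.00 | 10% vs 5% | ×2 | 55/28 | 1.00 | 0.92 | 1.04 |
| 1.00 | 10% vs 5% | ×3 | 55/29 | 1.00 | 0.92 | 1.06 |
| 1.00 | 5% vs 10% | ×1 | 29/55 | 1.00 | 1.09 | 1.00 |
| 0.80 | 10% vs 5% | ×3 | 65/31 | 0.80 | 0.73 | 0.85 |
| 0.70 | 5% vs 5% | ×1 | 35/32 | 0.70 | 0.71 | 0.70 |
| 0.70 | 10% vs 5% | ×1 | 71/33 | 0.70 | 0.64 | 0.70 |
| 0.70 | 5% vs 10% | ×1 | 38/64 | 0.70 | 0.79 | 0.70 |

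Reading the rows:

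- At 10% vs 5% the Fine-Gray figure stays at 0.92 while the complete-follow-up HR moves from 1.00 to 1.06. Counting the early losses in both arms as deaths gives 1.14, the opposite direction.
- Results nominally favouring talimogene laherparepvec at two-sided 0.05, with true HR 1.00 and harmless loss: 12.8% against 2.2% for the log-rank test at 10% vs 5%, and 5.5% against 2.5% at 7.5% vs 5%. Reversed (5% vs 10%), 12.2% nominally favour placebo.
- These cutoffs fall at about 50 to 61 months; Table 9, which also draws on external event projections, expects month 75. With a 75-month cutoff, 10% vs 5% gives 0.88.

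**The case against.** The strongest reply is that this is a descriptive supplement, read beside the primary HR. The stratified log-rank tests, the alpha allocation and the primary estimates do not use it, so the rejection percentages above show only how far the result can drift; they are not error rates of the trial. That stands.

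The follow-up summaries by arm and Clark's index would expose unequal follow-up, and a gap between Fine-Gray and Cox would itself hint at it. That also stands, but these outputs are descriptive. None re-estimates the treatment effect under a different assumption about lost subjects. Continued survival follow-up after stopping treatment (protocol 8.1) and searches of public records where permitted (protocol 12.4) should reduce OS loss without making the method valid.

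The sizes rest on assumed loss rates in a double-blind trial with one stated rate. That is fair: the milder 7.5% vs 5% case moves the HR only to 0.96.

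Four stronger readings are tempting and not supported:

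- That the primary inference is compromised. It is not.
- That loss to follow-up is otherwise ignored. Section 10.5.1.1 describes it, and iPFS has an extra imputation for unconfirmed iPD.
- That the arm losing more subjects always looks better. The driver is the rate: at HR 0.70 with equal 5% loss, talimogene laherparepvec loses more subjects (35 against 32), yet Fine-Gray moves slightly towards 1 (0.707).
- That the local-recurrence example in C.8 is a separate defect. It reads as a generic template comment.

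**Conclusion.** The point holds as a defect in a sensitivity analysis. The planned Gray and Fine-Gray comparison cannot assess informative censoring, because its result depends on how often each arm is lost and not on what happens afterwards. For OS it is the only analysis of loss to follow-up that estimates an effect, since the IPCW addresses subsequent therapy alone.

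It can err either way. Higher loss on talimogene laherparepvec gives false reassurance (0.92 for a true 1.00 at 10% vs 5%). Higher loss on placebo makes a sound result look fragile (0.79 for a true 0.70 at 5% vs 10%). With equal loss it nearly matches Cox, but that agreement would be no evidence that loss is harmless.

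The mechanism needs no assumption beyond the SAP's own coding. The sizes depend on assumed arm-specific loss rates and an unstratified approximation for OS; PFS and iPFS were not part of this simulation.

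**What to change.** Amend SAP 10.5.4.2, and 10.5.4.1 through its cross-reference, before unblinding:

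1. Stop using Gray's test and the Fine-Gray model as the informative-censoring check. Deletion is not essential: if kept, label the analysis and C.8 as cumulative incidence of recorded events, with no inference about robustness to informative censoring.
2. Keep the administrative/informative classification and tabulate type (2) censoring by arm.
3. Add a tipping-point analysis. Multiply impute event times after type (2) censoring, with the post-censoring hazard multiplied by a prespecified range of delta (for example 1, 1.5, 2, 3 and 5), once in both arms and once in the talimogene laherparepvec arm only. Analyse each completed data set with the primary stratified log-rank test and Cox model, and report the delta at which the conclusion changes.
4. Add a bound that counts type (2) censoring in the talimogene laherparepvec arm as an event at the censoring date.

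The cost is SAP wording and modest extra programming; no new data, visits or subjects are needed. The downside for the sponsor is a sensitivity result that may look less favourable.
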